Preliminary Telehealth Model for Intervention Delivery. The proposed intervention will begin with implementing routine screening for depression and suicidality in adult HIV care at the 3 study sites. The screening tools, the PHQ-2 and Columbia-Suicide Severity Rating Scale (C-SSRS), contain 8 items assessing depression and suicidality in the past month, including thoughts, intent, plan, and actions. The PHQ has been validated in Tanzania. We propose to validate several additional study measures in a preliminary validation study with 80 patients living with HIV and experiencing suicidal ideation: the HIV Stigma Scale (HSS), Beliefs About Medicines Questionnaire (BMQ), Illness Cognition Questionnaire (ICQ), Columbia-Suicide Severity Rating Scale (C-SSRS), self-Efficacy to Avoid Suicidal Action Scale (SEASA), Beck Hopelessness Scale-Short Form (BHS-SF), and Brief Reasons for Living Scale (BRFL).

Patients who endorse depressive symptoms only will receive brief supportive counseling to identify coping strategies and a referral for mental health services. Patients who screen positive for suicidal ideation (respond "yes" to any C-SSRS item) will be eligible for enrollment in the pilot clinical trial.

Once consented, the study team will assist patients to make a video call to the telehealth hub using a mobile phone. Video calls will be made using WhatsApp, a freely available, secure, and widely used mobile application with end-to-end encryption. Calls will be made free of charge (without data charges) using Wi-Fi hotspots made available at each study clinic. Patients who do not have an Internet-equipped phone will use study-owned phones. Private space will be provided in the research offices at each clinic for video calls

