Supplementary Aim: First, all study measures will undergo a thorough process of translation, backtranslation, and discussion to consensus with a team of bilingual researchers. Using the same recruitment procedures and eligibility criteria described in Aim 1, nurses will implement suicide screening during HIV clinic appointments. Patients (n=80) who screen positive for suicidality (i.e., respond "yes" to any C-SSRS item) will be notified of the research and, if interested, provide informed consent. Eligible participants who are not interested in participanting will receive referrals and resources for mental health support. After providing consent, participants will complete the translated survey measures administered by trained study staff. These data will be used to validate the study measures in the Tanzanian clinical context through evaluation of internal consistency (Cronbach's alpha and item-scale correlation), convergent validity among related measures, and confirmatory factor analysis. Participants will receive an incentive of 10,000 TZ shillings (\$4.50) to compensate for time and transport. Data collection for this Aim was completed in October 2022.

Aim 2: Refine content for the telehealth intervention with support from a study advisory board in Tanzania. The Duke PI will form an advisory board consisting of PLWH, nurses, mental health workers, administrators and local and regional government officials, to assist in refining the intervention. The advisory board will have approximately 15 members and will convene 3 times: 1) at the conclusion of Aim 1 to assist in refining the intervention prior to piloting by interacting with a prototype model, 2) midway through the clinical trial to review progress, and 3) at the conclusion of the trial to review and assist in interpreting findings. Key members of our previous KCMC advisory boards would be invited to continue their involvement for the current study.

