Employing principles of user-centered design and an experimental therapeutic approach, study personnel will invite advisory board members to experience the intervention as a study participant would, by interacting with the intervention technology, counselors, and study surveys. The process will include eliciting continual, iterative feedback on the hypothesized mechanisms of change, to adapt the intervention model to the study-specific context. Board members will observe as a mock patient completes screening and informed consent procedures, then uses a mobile phone to connect with an off-site counselor to participate in a mock counseling session. The board will give feedback on the process and perceived effectiveness of the session, as well as potential drawbacks. Through this process, we will reshape the intervention in real time, identifying opportunities to improve the intervention and increase potential acceptability for both clinic staff and patients.

Using advisory board feedback, the study team will develop a detailed study protocol and intervention manual. Counselors will be trained research nurses with an understanding of mental health and counseling skills. Counselor training will be provided by the Duke PI (a licensed psychologist) and the consulting psychiatrist and will consist of 3 weeks of didactic and mock intervention sessions. This will include instruction in counseling skills, the intervention model, and ethical/safety considerations for research and counseling. During mock sessions, counselor skills and fidelity to the intervention will be assessed by the supervisors using an adapted Therapy Quality Scale (TQS), interrater reliability will be calculated, and disagreement > 1 point will be discussed to consensus. Counselors will be required to attain mean TQS scores \geq 3 (on a 0-4 scale) in mock sessions prior to contact with participants. They will then complete supervised trial runs with 5 patients from the study clinics, which will be used to refine and finalize the intervention prior to starting enrollment in the clinical trial.

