Aim 3: Pilot test the telehealth intervention in a randomized controlled trial to assess feasibility, acceptability, and potential efficacy for reducing suicidality and enhancing HIV care engagement. To evaluate the intervention, the study team will enroll 60 PLWH in a Stage I pilot feasibility trial. Participants will be adults who experienced suicidal ideation in the past month seeking HIV care at one of the 3 study clinics. Using the same recruitment procedures and eligibility criteria described in Aim 1, nurses will implement depression and suicide screening during HIV clinic appointments. Patients who screen positive for depression, but not suicidality, will not be eligible for the clinical trial but will receive a brief supportive counseling module based on WHO's Problem Management+ and a referral for further mental health support. Patients who screen positive for suicidality (i.e., respond "yes" to any C-SSRS item) will be referred to study staff, notified of the research and, if interested, provide informed consent. Eligible participants who are not interested in participating will receive referrals and resources for mental health support.

After providing consent, participants will complete a baseline survey administered by trained study staff. Participants will receive an incentive of 10,000 TZ shillings (\$4.50) for each session at the clinic to compensate for time and transport. Participants who connect to calls from a location other than the clinic will receive 10,000 TZ shillings if connecting via video call (to compensate for time and data costs) and 5,000 TZ shillings if connecting by telephone call (as incoming calls will not incur costs to participants). Data collected at baseline will include measures of suicidality, HIV care engagement, and covariates such as stigma, social support, and quality of life. For measures not previously validated in Tanzania, the study team will complete a thorough linguistic and cultural translation process as established by Beaton et al., including back translation, validity checks, and piloting.

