Feasibility and acceptability of the intervention will be described by retention patterns, participant satisfaction, fidelity, and implementation cost. *Participant satisfaction* will be measured using the Client Satisfaction Questionnaire⁹³ at the 3-month survey and defined as a mean score \geq 3 on a 1-4 scale. *Fidelit y* to the manual will be measured by TQS and deemed acceptable if mean scores are \geq 3 on a 0-4 scale. *Co st* of the intervention will be tracked, including the time for training, supervision, and actual costs incurred.

Potential efficacy will be assessed by analyzing differences by condition in primary outcomes (suicidality, HIV care engagement, viral load) and secondary outcomes (depression, social support, quality of life). The trial will not be powered to detect significant intervention effects or stable effect sizes; however, we will conduct these analyses to examine the potential for effects in a larger trial. Mixed-effects regression will be used to model pre-post differences within and between arms using a time by condition model specification (time, condition, and time*condition). Individual-level random intercepts will be used to account for correlation due to repeated measurement. This mixed-effects regression approach allows us to control for baseline outcome values that may not be balanced between groups due to small sample size, and may improve precision of treatment effect estimates. We will also generate parameter estimates and ranges of values to estimate power for a future larger clinical trial study.

Data & Safety Monitoring

• Summarize safety concerns, and describe the methods to monitor research subjects and their data to ensure their safety, including who will monitor the data, and the frequency of such monitoring. If a data monitoring committee will be used, describe its operation, including stopping rules and frequency of review, and if it is independent of the sponsor (per 45 CFR 46.111(a) (6)).

The Duke PI [name] will receive guidance on research with patients at-risk of suicide in monthly mentoring meetings with [name], a recognized expert in the field of suicide prevention research. During these meetings, Drs. [name] and [name] will review safety data from the study, including trends in suicidal ideation and any reported instances of suicidal behavior or death by suicide

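### Is HIV care engagement, one of the pilot's three primary outcomes, left too undefined to analyse?

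*Combined protocol and SAP*

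**What the plan says.** The analysis section lists "primary outcomes (suicidality, HIV care engagement, viral load", and then depression, social support and quality of life as secondary outcomes. One model serves them all: "Mixed-effects regression will be used to model pre-post differences within and between arms using a time by condition model specification". It adds that "We will also generate parameter estimates and ranges of values to estimate power for a future larger clinical trial study", having just said that the trial is not powered for significant effects or stable effect sizes.

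Engagement is otherwise mentioned as something measured only under Aim 3: "Data collected at baseline will include measures of suicidality, HIV care engagement, and covariates such as stigma, social support, and quality of life". That sentence belongs to a paragraph that opens with a survey given by study staff, completed before randomisation.

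The one dated follow-up is in the feasibility paragraph, where satisfaction is assessed "at the 3-month survey and defined as a mean score" of at least 3. Data & Safety Monitoring refers to an undated follow-up survey, in the singular, for suicidality. Risk/Benefit Assessment mentions medical record review, but only as a confidentiality risk.

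**The concern.** Improved engagement is in the study title, the hypothesis and Aim 3, so one expects to be told what it is: visits kept, retention, adherence or a scale score. The feasibility paragraph makes the gap more visible, because satisfaction there has an instrument, a time, a scale and a threshold, while this primary outcome has none.

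Three things could go wrong. The measure might be chosen after the arms had been compared. A survey and a clinic record might disagree, because people who leave HIV care may also miss the survey. And a poorly founded estimate could then enter the next trial's power calculation.

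**Working it through.** The plan gives no figure to reproduce for this outcome, so the check sets the passages side by side and then sizes the worst case under stated assumptions.

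**1. What is and is not stated**
- Baseline time: stated (Aim 3).
- Source: a survey by context, not outright. Record review is mentioned elsewhere but linked to no outcome.
- Follow-up time: not tied to engagement. A pre-post model, one dated survey (3 months) and a singular follow-up survey all point to one post-baseline value at 3 months.
- Variable and scale: not stated.

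**2. Whether the list of instruments shows that no measure exists**

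Ten instruments are named: eight under the Preliminary Telehealth Model, plus the Therapy Quality Scale and the Client Satisfaction Questionnaire. None is described as measuring engagement. But the Preliminary Telehealth Model names two screening tools and a set of measures needing local validation ("the HIV Stigma Scale (HSS), Beliefs About Medicines Questionnaire (BMQ), Illness Cognition Questionnaire (ICQ), Columbia-Suicide Severity Rating Scale (C-SSRS" and three others). It does not present a full outcome battery. Social support and quality of life have no named instrument either, and viral load has no stated source or follow-up time.

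The remark on the validation study, "Data collection for this Aim was completed in October 2022", does not settle the matter. A visit count or an already validated scale would need no such study, and Aim 3 provides separately for translating and piloting measures not yet validated in Tanzania.

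**3. How far the source could matter (invented figures)**

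Suppose 6 of 30 control and 3 of 30 intervention participants are out of care. A complete record gives 24/30 = 80% against 27/30 = 90%, a difference of +10 points. A survey of those who return gives:
- all 9 return: 80% against 90%, +10
- none of the 9 returns: 24/24 against 27/27, 0
- only the 3 intervention participants return: 24/24 against 27/30, -10
- only the 6 controls return: 24/30 against 27/27, +20

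The -10 and +20 need all-or-none return that differs completely by arm. Nothing in the document supports such a pattern, or shows that a record would cover all 60.

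**4. How far choosing afterwards could matter**

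With 30 per arm, complete data and pre-post correlation r, the standard error (SE) of the time-by-condition contrast in SD units is sqrt(2(1-r)) x sqrt(2/30). At r = 0.5 this is 1 x 0.258 = 0.258. With no true effect, the larger of two estimates whose correlation is c has expectation SE x sqrt((1-c)/pi):
- c = 0: 0.146
- c = 0.5: 0.103
- c = 0.8: 0.258 x sqrt(0.2/3.1416) = 0.065
- c = 1: 0

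Two measures of the same construct in the same people should be well correlated, so the upper value is not realistic. The 95% half-width is 1.96 x 0.258 = 0.51 SD. Even 0.146 is under a third of that (0.146/0.51 = 0.29).

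**The case for a change.** The strongest case for a change is that the form's own prompt asks for endpoints to be described, that a primary outcome deserves at least what satisfaction receives, and that an arm comparison used for later planning needs a defined variable. The scale also decides between a linear and a generalised mixed model.

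Part of this stands. A reader of this document alone cannot say what the engagement variable is, and the 3-month reading is an inference. The wording also allows for more than one measure.

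The rest carries less weight. The document is an institutional review application, and under Aim 2 it says that "the study team will develop a detailed study protocol and intervention manual". That protocol is not available here, so a choice made after seeing results is a possibility and not something shown. Mixed-effects regression covers both linear and generalised forms, and the analyst picks by scale. Loss of people who leave care is a real limit of survey data, but naming the survey as the source would not remove it, and retention is itself reported as a feasibility result. One might also fear that the two extra scheduled intervention sessions (3 against 1) would count as HIV visits. No passage makes attendance the measure, and the nurse-counselors document these sessions in the study's own database.

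**Conclusion.** The gap is one of documentation, and no change to the plan follows. No stated rule gives a wrong result. The sensible analysis can be read from what is there: the engagement measure taken before randomisation, repeated at the 3-month survey, in the time-by-condition model.

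The possible harm is small for this trial's purpose. Picking the larger of two null estimates would add about 0.065 SD at c = 0.8 and 0.146 SD at the implausible c = 0, and nothing if the measure was fixed beforehand. The half-width is about 0.51 SD. These figures assume r = 0.5, 30 per arm and no dropout. The plan already treats its effect estimates as unstable and promises ranges for the next trial's power, not one number.

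The conclusion rests on two readings that the document supports but does not spell out: a single follow-up at 3 months, and outcome detail held in the fuller protocol.

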Assignment to condition. Upon completion of the baseline survey, participants will be individually randomized to receive either a brief Safety Planning Intervention (n=30), or the 3-session telehealth intervention (n=30). Participants will be randomized at a 1:1 ratio using a block randomization method (4 per block) to ensure equal sample sizes in each condition and to manage the flow of participants to the intervention condition. The allocation sequences will be prepared ahead of time using an online randomization program.

Intervention and control procedures. After randomization, participants will be guided to a private space and assisted to connect by video call to the nurse-counselor (based at KCMC). Upon connecting, control participants will receive the brief (20 minute) Safety Planning Intervention and intervention participants will complete the first of 3 telehealth-delivered counseling sessions. For intervention participants, the remaining sessions will be scheduled at two-week intervals. Patients unable to come to the clinic for followup sessions will be given the option to connect via video call or telephone call from the location of their choice. For participants in both conditions, prior to ending the call, the counselor will re-administer the C-SSRS and those at risk of suicide will be directly referred for psychiatric assessment and treatment to ensure their safety. Participants in both conditions will receive text message check ins from the counselors to inquire about their well-being and connect them to additional support as needed. Participants in both conditions will also have the opportunity to contact the telehealth counselors at any time during normal business hours for additional support throughout their participation in the study. These 'booster sessions' will be focused on assessing suicide risk, safety planning, and reinforcing prior session content.

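### The planned time-by-condition contrast subtracts the chance baseline gap instead of conditioning on baseline; a common-baseline or ANCOVA contrast is usually more precise at almost no cost

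*Combined protocol and SAP*

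**What the plan says.** Data Analysis & Statistical Considerations describes one between-arm efficacy model. Mixed-effects regression will "model pre-post differences within and between arms", "using a time by condition model specification (time, condition, and time*condition"), and "Individual-level random intercepts will be used to account for correlation due to repeated measurement". The stated reason is: "This mixed-effects regression approach allows us to control for baseline outcome values that may not be balanced between groups due to small sample size". The same sentence adds that precision may improve. No section adds a baseline covariate, an ANCOVA, or a constraint that the arms share one baseline mean.

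The section is open about the limits of a pilot: "The trial will not be powered to detect significant intervention effects or stable effect sizes". It still gives the estimates a use: "We will also generate parameter estimates and ranges of values to estimate power for a future larger clinical trial study".

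On the available data, Design & Procedures, Aim 3 states: "Data collected at baseline will include measures of suicidality, HIV care engagement, and covariates such as stigma, social support, and quality of life". The paragraph on assignment to condition fixes the order: "Upon completion of the baseline survey, participants will be individually randomized".

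**The concern.** With a condition main effect in the model, each arm has its own free baseline mean and baseline is treated as one more outcome. In a linear pre-post model, the interaction is then a difference in change scores. That nets out a baseline imbalance by subtraction, which is not the same as conditioning on baseline. Scores that start high by chance tend to drift back, so only part of a chance gap persists to follow-up, and subtracting all of it over-corrects.

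The sponsor names small-sample imbalance as the reason for the model, yet the planned estimate remains correlated with that imbalance. At stake is some precision in a 60-person trial whose estimates are meant to inform a larger one.

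A lesser point is that a random intercept alone assumes the same SD at both times. Enrolment requires a positive C-SSRS (Selection of Subjects), which makes that assumption doubtful for suicidality scores.

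**Working it through.** **Inputs from the documents.** 60 participants, 30 per arm, 1:1 in blocks of 4, baseline survey before randomisation, pre-post model. No SD, correlation, alpha, effect size or dropout rate is given, so there is no power figure to reproduce; only 30 + 30 = 60 can be checked.

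**Assumptions.** Normal scores, linear model, one follow-up, no true effect. Let b be the slope of follow-up on baseline, s0² the baseline variance, r² the residual variance of follow-up given baseline, n = 30 per arm, and D the observed baseline gap. Before any selection, both SDs are 1, so b equals the correlation (0.3, 0.5, 0.7) and r² = 1 − b².

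**Step 1: what the interaction estimates.** With complete data it equals the difference in mean change exactly; this was confirmed by refitting the mixed model to simulated trials. Given D, the follow-up difference is expected to be (true effect) + bD. Subtracting D leaves (true effect) − (1 − b)D. Averaged over randomisations D is zero, so there is no bias, but the error given D is −(1 − b)D.

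**Step 2: how large D is.** Its SD is √(2/30) = 0.258 baseline SDs. The mean absolute gap is 0.258 × √(2/π) = 0.206. P(|D| > 0.3) = 2[1 − Φ(0.3/0.258)] = 0.245, and P(|D| > 0.5) = 0.053. With equal SDs, a gap of 0.3 shifts the planned estimate by 0.7 × 0.3 = 0.21, 0.5 × 0.3 = 0.15 or 0.3 × 0.3 = 0.09 SD. This shift is already inside the planned SE, as (1 − b)/2 = 35%, 25% or 15% of its variance. It is not an added bias.

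**Step 3: variances.**
- Planned: (2/n)[r² + (1 − b)² s0²]
- Baseline-adjusted: (2/n) r² [1 + 1/(2n − 4)], where the last factor is 1 + 1/56 = 1.018

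Equal SDs, b = 0.5: planned SE = √[(2/30)(0.75 + 0.25)] = 0.258; adjusted SE = √[(2/30)(0.75)(1.018)] = 0.226; variance ratio 1.31.

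Narrowed baseline (cut at the mean, s0² = 1 − 2/π = 0.363), b = 0.3: ratio = (0.91 + 0.49 × 0.363)/(0.91 × 1.018) = 1.17; without the small-sample factor, 1.20.

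Narrowed baseline (cut at +0.5 SD, s0² = 1 − 1.141 × 0.641 = 0.269), b = 0.3: ratio = (0.91 + 0.49 × 0.269)/(0.91 × 1.018) = 1.12.

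**Step 4: results.** Simulated values come from 20,000 trials per setting, with the planned model fitted by REML.

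| | b = 0.3 | b = 0.5 | b = 0.7 |
|---|---|---|---|
| Equal SDs, complete: SE planned | 0.306 | 0.258 | 0.200 |
| Equal SDs, complete: SE adjusted | 0.248 | 0.226 | 0.186 |
| Variance ratio, formula | 1.51 | 1.31 | 1.16 |
| Variance ratio, simulated | 1.49 | 1.30 | 1.14 |
| Equal SDs, 20% dropout, simulated | 1.41 | 1.24–1.25 | 1.12 |
| Narrowed baseline, complete, simulated | 1.12–1.18 | 1.07–1.10 | 1.03–1.05 |
| Narrowed baseline, 20% dropout, simulated | 1.09–1.15 | 1.05–1.10 | 1.02–1.06 |

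The narrowed rows span both cuts; the dropout rows span random and baseline-dependent dropout. A second simulation with random dropout gave 1.36, 1.22 and 1.11 for equal SDs.

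In sample-size terms, under the planned contrast 60 participants are worth 60/1.15 = 52 to 60/1.02 = 59 in the last row. With equal SDs and complete data (formula) they are worth 60/1.51 = 40, 60/1.31 = 46 and 60/1.16 = 52.

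**Step 5: dependence on the gap.** With equal SDs and complete data, the simulated slope of the planned estimate on D was −0.70, −0.49 and −0.29. For the adjusted estimate it stayed within 0.03 of zero in every setting. Both estimators were unbiased.

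**Step 6: where the gain runs out.** It vanishes as b approaches 1. If the follow-up SD is 1.25 times the baseline SD, there is no gain for correlations of about 0.71 to 0.86, and the adjusted contrast costs at most about 1% of SE.

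**Step 7: the precision remark.** With complete data, the planned contrast beats a follow-up-only comparison when b exceeds 0.5. The remark that precision may improve is therefore incomplete, not false.

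**The case against.** The planned model is valid, unbiased, and answers the pre-post question the plan asks. The trial is openly unpowered, and no decision rule uses the coefficient. With equal SDs and 20% dropout, the SEs are 0.333, 0.283 and 0.221 planned against 0.281, 0.254 and 0.209 adjusted. Multiplied by 1.96, the half-widths are 0.65 against 0.55, 0.55 against 0.50, and 0.43 against 0.41 SD. All are too wide to settle an effect size. The larger ratios assume equal SDs, the very assumption that is doubtful for suicidality, where the gain is only 2% to 15% of variance with dropout. No outcome has a stated scale. If suicidality were coded as any ideation yes or no, baseline would be nearly constant and the point would largely disappear. Saying that the model controls for baseline is loose, but a change score does subtract the gap.

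All of this stands, and it limits the weight of the point without removing it. Scales not used for selection, such as quality of life or social support, may lie nearer the equal-SD rows. Low power is no reason to give up precision that needs no new data.

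Two supporting arguments deserve little weight. Under the narrowed-baseline settings, the random-intercept correlation differs from the true one by only 0.02 to 0.04, against a sampling SE of about 0.10 to 0.13. The common-baseline model does retain participants without follow-up, but in simulated data sets with complete baselines its between-arm estimate equalled completer ANCOVA; retention helps only the within-arm change.

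**Conclusion.** The concern holds for outcomes analysed with a linear model. The specified interaction is the difference in mean change (exactly with complete data, approximately with dropout), and it does not condition on baseline as the plan's sentence suggests. The excess variance is about 2% to 15% where eligibility narrows the baseline and 20% drop out. It is 14% to 49% with equal SDs and complete data, and it shrinks to nothing as b approaches 1.

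These sizes rest on assumed correlations of 0.3 to 0.7, normal scores and a single follow-up, none of which the documents supply. The identity is not exact for binary or count models. This is a recommended improvement to the only efficacy model described. It does not threaten the trial's validity.

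**What to change.** Preferred: fit a repeated-measures model with time and the time-by-condition interaction but no condition main effect, so the arms share one baseline mean, and use unstructured covariance so SDs can differ by time. The shared mean is justified because baseline precedes randomisation. The model still yields the within-arm changes the plan promises.

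Alternative: use ANCOVA of follow-up on condition and baseline for the between-arm effect, and keep the existing model for within-arm change.

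Replace the sentence about controlling for baseline with, for example: between-arm effects will be estimated with a common baseline mean and unstructured covariance, so that they condition on observed baseline values.

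State the scale of each outcome. For binary or count outcomes, name the matching baseline-adjusted model and its effect measure. Report the pre and post SDs and their correlation for planning the larger trial.

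The cost is two or three lines of text and no new visits. The Aim 3 list names baseline suicidality, HIV care engagement, social support and quality of life; it does not name viral load or depression, so their baseline values should be confirmed. The planned model needs them too. Small downsides: unstructured covariance adds one variance parameter, ANCOVA alone gives no within-arm change, and a baseline-adjusted odds ratio is a conditional measure.
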